# 7.2.4 Reporting of SAE to IRB

All SAEs occurring on this study will be reported to the IRB according to the IRB policy,. For WCM investigator-initiated studies, the following reporting guidelines apply:

a. A Mandatory MedWatch Form 3500A must be completed and sent to the FDA. Specific instructions on how to complete the MedWatch Form 3500A can be found on the FDA website.

b. If the protocol requires SAEs to be reported to an outside agency (i.e., to the supplier of the study drug), specific instructions will be stated in the protocol.

c. If the study utilizes the WCM Data and Safety Monitoring Board (DSMB), a narrative of the event will be submitted to the Regulatory Coordinator on a modified SAE cover sheet. The completed form serves as acknowledgement of the SAE's occurrence and will be used to complete the DSMB periodic report. A copy should be filed in the regulatory binder.

d. For multicenter studies, the multicenter core within the Quality Assurance Unit (QAU) will distribute the IND Safety Report

# 7.2.5 Notification of Serious Adverse Event to Oncolys

An SAE must be reported by the Investigator within 24 hours of discovery if it occurs during the clinical study or within 28 days of receiving the IP, whether or not the SAE is considered to be related to the IP. An SAE report consists of the SAE form, the AE form, and the concomitant medication form. A copy of these forms must be e-mailed to the attention within 24 hours of discovery:

#### E-mail: [contact]

Please note: If the SAE can be categorized into one or more of the "Outcomes Attributed to the Adverse Event" outlined on the Mandatory Medwatch form 3500, the form and SAE Cover Sheet will be submitted to WCM Quality Assurance Unit (QAU) within 24 hours of PI notification.

The primary site will submit the Mandatory Medwatch form 3500 to Oncolys, Inc within 72 hours of receiving the form and to the FDA as specified by FDA guidelines.

The Investigator should not wait to receive additional information to document fully the event before notification of a SAE, though additional information may be requested. Where applicable, information from relevant laboratory results, hospital case records, and autopsy reports should be obtained.

Instances of death, congenital abnormality, or an event that is of such clinical concern as to influence the overall assessment of safety, if brought to the attention of the Investigator at any time after cessation of IP administration and linked by the Investigator to this study, should be reported to.

All SAEs must be reported to the investigational site's IEC/IRB by the Investigator in accordance with their regulations.

Reporting of any SAEs to applicable regulatory authorities will be the responsibility of Oncolys BioPharma Inc. in compliance with local regulations.

Details of the procedures to be followed if a pregnancy occurs are provided in Section7.2.7.

## 7.2.6 Notification of Suspected Unexpected Adverse Reactions

An unexpected adverse reaction is any untoward and unintended response that is related to the administration of the IP at any concentration that is not consistent with the applicable version of the Investigator's Brochure .

All suspected unexpected serious adverse reactions (SUSARs) will be the subject of expedited reporting in accordance with local requirements. All Investigators should follow-up SUSARs until the event is resolved or until, in the opinion of the Investigator, the event is stabilized or determined to be chronic. Post study SAEs that are deemed to be related to IP that occur after the patient has completed the clinical study must be reported by the Investigator to Oncolys BioPharma Inc.

#### 7.2.7 Notification of Pregnancies

All pregnancies in female patients and female partners of male patients receiving IP will be recorded from treatment until 90 days after the patient has completed therapy.

Should a patient or male patient's partner become pregnant or suspect she is pregnant while participating in this study, or in the 90 days following when the patient received the last injection of IP, the treating Investigator should be informed immediately. All pregnancies will be reported on a pregnancy report form and submitted to safety along the same timelines as an SAE.

The IEC/IRB and Oncolys BioPharma Inc. will be informed. The patient will be asked to provide information on the outcome of the pregnancy, including premature termination should the case arise. For pregnancies in a female partner of a male patient consent to follow-up on the pregnancy will be obtained in agreement with the US Health Insurance Portability and Accountability Act (HIPAA) and other local laws and regulations as outlined in Section. Pregnancy outcomes will be reported on a pregnancy follow-up report form.

Spontaneous miscarriage and congenital abnormalities will be reported as SAEs The Follow-up Period for any and all pregnancies will be deemed to have ended when the health status of the child has been determined on its birth and followed up for 8 weeks after the birth for any potential abnormalities.

Full details will be recorded on the withdrawal page of the eCRF.

#### 7.3 Multicenter Study Monitoring

The study will be monitored by the Weill Cornell Multicenter Study group, according to the Clinical Trial Monitoring Plan, which addresses site qualification, regulatory documentation, and site monitoring and auditing.

## 8 STATISTICAL ANALYSES

#### 8.1 General Considerations

Full details of the statistical analysis will be provided in a statistical analysis plan (SAP). Any changes to the planned statistical methods from the SAP will be documented in the clinical study report (CSR). The statistical evaluation will be performed using SAS®, version 9.4 or later.

All data will be presented in listings, ordered by patient, unless otherwise specified.

Descriptive statistics for continuous variables (number of patients [n], number of patients with missing data, mean, standard deviation, minimum and maximum) and categorical data (n, percent, number of patients with missing data, by category) will be presented.

#### 8.2 Definitions for Statistical Data Analysis

The following definitions were used in the assessments of safety and efficacy.

All patients who receive at least one injection of OBP-301 will be included in the Safety Population and are analysed according to the actual treatment received. Any patient that has at least one radiographic assessment for response will be included in the Efficacy Population.

#### 8.3 Handling of Missing Values and of Values outside the Detection Limits

Missing values will not be imputed. All missing values will be reported in the listings as either "missing" or as the justification for the value being missing (e.g., "ND" [test not done] or "BQL" [below quantitation limit], where appropriate.

While efforts will be made to avoid incomplete or missing data, in rare cases the AE date could be incomplete or missing. If this happens, incomplete or missing dates will be imputed. For the calculation of AE duration and AE onset from dosing, missing AE dates will be imputed using a conservative approach. This approach will assume that the AE is treatment emergent where insufficient date information exists to determine if the AE occurred before or after dosing, except where year is missing. If the year is also missing then it will be assumed that the start is before the start of the study.

Imputed onset dates of AEs will be checked to ensure they occur after the first study day and before the resolution date. Imputed resolution dates will be checked to ensure they occur after the onset date and before date of last study visit (where AE is not flagged as ongoing).

Descriptive statistics for demographics, body weight, vital signs, and ECG data will be calculated from actual data only, with the number of actual data points used for the calculation of the summary statistics reported.

For censored safety lab data (i.e., hematology, clinical chemistry and urinalysis results that are outside the limit of quantification) the actual values reported by the laboratory (e.g., "< 2" for bilirubin) will be presented in the data listings. For the calculation of summary statistics, safety laboratory data values below the lower limit of quantification (LLOQ) will be set to  $\frac{1}{2}$  the LLOQ.

# 8.3.1 Data Collection

The data collection plan for this study is to utilize REDCap to capture treatment, toxicity, efficacy, and adverse event data for all enrolled patients.

# 8.3.2 REDCap

REDCap (Research Electronic Data Capture) is a free data management software system that is fully supported by the Weill Cornell Medical Center CTSC. It is a tool for the creation of customized, secure data management systems that include Web-based data-entry forms, reporting tools, and a full array of security features including user and group based privileges, authentication using institution LDAP system, with a full audit trail of data manipulation and export procedures. REDCap is maintained on CTSC-owned servers that are backed up nightly and support encrypted (SSL-based) connections. Nationally, the software is developed, enhanced and supported through a multi-institutional consortium led by the Vanderbilt University CTSA.

# 8.4 Analysis Populations

# 8.4.1 Safety Population

All patients who receive at least one injection of OBP-301 will be included in the Safety Population and are analysed according to the actual treatment received.

# 8.4.2 Evaluable Population

Any patient that has at least one radiographic assessment for response will be included in the Efficacy Population. Imaging studies preferably CT scan of the chest/abdomen/pelvis will be performed every 9 weeks as per the study schedule. Patients will be evaluated according to RECIST v1.1 criteria. Definitions of response evaluation are detailed in section 6.6 for further explanation. Only those patients whose response can be measured according to RECIST v1.1 will be included in this population.

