Investigational Product Administration:	OBP-301, the investigational product (IP) is formulated in 20 mM Tris pH 8.0, 25 mM NaCl with 2.5% glycerin, USP by volume. OBP-301 will be injected into the target tumor lesions.
Planned Patients:	41 patients in total for both stage 1 and 2, to achieve 37 evaluable patients.
Participant Selection	Inclusion Criteria:
Criteria:	Patients who meet all of the following criteria will be considered for inclusion in the study:
	
 
Be willing and able to provide written informed consent for the trial.
 
Be ≥18 years of age on the day of signing the informed consent.
 
Have an Eastern Cooperative Oncology Group (ECOG) performance status of 0-2.
 
Have histologically or cytologically confirmed advanced or metastatic gastroesophageal adenocarcinoma, at least 1 cm in size and amenable to intratumoral injection.
 
Patient must have received at least 2 line of systemic therapy for advanced disease.
 
Tumor must be PD-L1 positive, as defined by a combined positive score (CPS).
 
Have one or more measurable lesions based on iRECIST.
 
Be willing to provide tissue; newly obtained biopsy specimens or formalin-fixed, paraffin-embedded (FFPE) block specimens.
 
Female subjects of childbearing potential have a negative urine or serum pregnancy test within 7 days prior to enrollment. If the urine test is positive or cannot be confirmed as negative, a serum
 

10.	pregnancy test will be required. If a serum pregnancy test is required it can be performed on the same day as the urine pregnancy test. The serum pregnancy test must also be completed 7 days prior to enrollment. And male / female subjects of childbearing potential must agree to use an adequate method of contraception starting with signing the informed consent through 120 days after the last dose of study medication. Demonstrated adequate organ function as defined in following criteria. All screening labs should be performed within 14 days of enrollment. Note: Subject must not have taken transfusion, hematopoietic agent; granulocyte-colony stimulating factor (G- CSF) etc., and/or oxygen supplementation within 7 days before the screening labs.

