#### 4.5 Stopping Criteria

#### 4.5.1 Patient Withdrawal Criteria

In accordance with applicable regulations, a participant has the right to withdraw from the study, at any time and for any reason, without prejudice to his future medical care.

Withdrawal from the study and therapeutic measures taken shall be at the discretion of the Investigator. A full explanation for the discontinuation from the study should be made in the participant's medical records and in the eCRF.

Premature discontinuation from active study participation may occur at any time due to any of the following reasons:

- Any situation where, in the opinion of the Investigator or the Medical Monitor, continued participation in the study would not be in the best interest of the patient.
- Positive pregnancy test (see Section for procedures to be followed in case of a pregnancy).
- Patient initiates other anti-cancer therapy. The anti-cancer therapy will be documented in the medical record and eCRF.
- Patient is unable or unwilling to comply with study procedures.
- Patient is lost to follow-up.
- Patient withdraws consent.
- Request by a Health Authority.
- Termination of the study by the study investigator(s).
- Progressive neoplastic disease, unless the Investigator feels this may be pseudoprogression, in which case the patient may remain on study until the next evaluation for extent of disease.

The reason(s) for premature study discontinuation/withdrawal should be reported in the eCRF and within the source documents along with the date of withdrawal. AEs should be documented according to Section 7.0 Adverse Events.

For all patients who discontinue, a Final Visit will be performed within  $28 \pm 5$  days after the last IP administration. If a participant is withdrawn because of an AE, the Investigator must arrange for the participant to have appropriate follow-up care until the AE is resolved or has stabilized. Unresolved AEs will be followed until the last scheduled follow-up visit or until the Investigator determines that further follow-up is no longer indicated. Investigators should attempt to collect the survival information as dictated in section 6.1.3.

Patients who discontinue the active study participation will not be replaced.

Any enrolled patients who are discontinued before study dosing will be documented as screen failures in the eCRF and replaced. No follow-up is required for these patients.

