# OBP-301

OBP-301 injection will be delayed for any ongoing Grade 3 toxicity attributable to OBP-301 at the time of the next scheduled injection. Patients who require a delay of OBP-301 injection of > 4 weeks (i.e., approximately 6 weeks from the previous injection) due to lack of resolution to

Grade 1 toxicity will be discontinued from the study. In this circumstance, the patient will be evaluable for toxicity, but will be replaced (up to the maximum enrollment) for efficacy assessment.

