# 8.8 Determination of Sample Size

Sample size is determined according to Simon's two-stage Minimax design. We project a RR of 15% (historical RR for pembrolizumab alone), below which the combination regimen will be unacceptable, and a RR of 30% (expected RR rate for OBP-301 + pembrolizumab), above which the combination regimen will be considered worthy of further exploration. The null hypothesis that the RR is less than or equal to 15% will be tested against the alternative hypothesis that the RR is greater than or equal to 30%.

The sample size computations were performed assuming a 10% level of significance and 80% power. If 2 or fewer patients respond out of the first 18 evaluable patients, the study arm will be terminated and declared to have a negative result. If 3 or more patients respond out of the first 18 evaluable patients, enrollment will be extended to 37 patients. The treatment will be declared effective and worthy of further testing if 9 or more patients respond among the 37 patients entered. This two-stage design yields a  $\geq 0.80$  probability of a positive result if the true RR is  $\geq 30\%$ . It yields a  $\geq 0.90$  probability of a negative result if the true RR is  $\leq 15\%$ . A 95% confidence interval constructed around the expected RR of 30% can be estimated to be within  $\pm 14.8\%$  of the observed RR proportion. Assuming 10% are unevaluable/ineligible, we anticipate that a total of 41 patients will be enrolled in the study (assuming the study proceeds to the second stage).

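### The go/no-go denominator leaves out treated patients who never have a response scan, so the stated 10% type I error is not protected

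*Combined protocol and SAP*

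**What the plan says.** **Decision rule.** Section 8.8 and the synopsis stop the trial if 2 or fewer of the first 18 evaluable patients respond. For the final analysis section 8.8 says: "The treatment will be declared effective and worthy of further testing if 9 or more patients respond among the 37 patients entered". The figure legend in section 3.1 describes those 37 as evaluable, and so does the synopsis: "41 patients in total for both stage 1 and 2, to achieve 37 evaluable patients".

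**Error rates.** "The sample size computations were performed assuming a 10% level of significance and 80% power". The test is one-sided: "The null hypothesis that the RR is less than or equal to 15% will be tested". The 15% is described as the historical rate for pembrolizumab alone. Nothing says whether that rate is among all treated or among evaluable patients. The step from 37 to 41 allows for 10% who are unevaluable or ineligible, as one pooled figure.

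**Who is evaluable.** Section 8.4.2: "Any patient that has at least one radiographic assessment for response will be included in the Efficacy Population", and further: "Only those patients whose response can be measured according to RECIST v1.1 will be included in this population". Section 6.6.3 puts re-evaluation imaging every nine weeks from the start of treatment. The schedule in section 6.1 also marks imaging at the end-of-study visit.

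**Missing response.** Section 8.3 does not impute missing values, and no section counts a missing response as a non-response. Section 8.4.3 defines an intent-to-treat set, but sections 8.5 and 8.8 do not tie it to the primary endpoint or the go/no-go rule.

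**Replacement.** Section 5.2.4 (OBP-301) says of a patient discontinued after a toxicity delay of more than 4 weeks: "the patient will be evaluable for toxicity, but will be replaced (up to the maximum enrollment) for efficacy assessment". Section 4.5.1 says: "Patients who discontinue the active study participation will not be replaced". Section 6.1.4 repeats the latter.

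**The concern.** This is a third- or fourth-line population with ECOG 0 to 2 and a required life expectancy of only 4 months or more. Some patients can be expected to die or deteriorate before a scan at week 9. They have had the treatment and have not responded. Leaving them out raises the observed response rate while the 15% reference stays fixed, so the bias favours the combination. It also weakens the stage 1 futility stop.

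Two further points leave the denominator open. Calling the final 37 both evaluable and entered gives two different rules when 41 are enrolled. Whether a patient is evaluable is also known only weeks after enrolment, so the evaluable number may not land on 37. Finally, replacing patients for efficacy because of the study drug's own toxicity is informative exclusion. Under section 8.4.2 such a patient with a scan stays in the Efficacy Population, while section 5.2.4 replaces the same patient.

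At stake is the only formal efficacy decision in the trial.

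**Working it through.** **Inputs.** From section 8.8: null rate 15%, target 30%, stage 1 n = 18 (stop at 2 or fewer), final n = 37 (positive at 9 or more), 10% unevaluable or ineligible, 41 enrolled.

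**1. The plan's own figures.** With X1 ~ Bin(18, p) and X2 ~ Bin(19, p):

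P(positive) = Σ over x ≥ 3 of P(X1 = x) × P(X2 ≥ 9 − x).

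- At p = 0.15 the terms for x = 3 to 8, then x ≥ 9, are 0.0129, 0.0230, 0.0248, 0.0168, 0.0073, 0.0021 and 0.0005. They sum to 0.0875 before rounding. The early-stop probability P(X1 ≤ 2) is 0.480.
- At p = 0.30 the sum is 0.806.
- A search over designs confirms 37 as the smallest total meeting 10% and 80%.
- The stated precision also reproduces: 1.96 × √(0.3 × 0.7/37) = 0.148. Enrolment is 37/0.9 = 41.1.

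The design is therefore correct if 15% and 30% are rates among evaluable patients.

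**2. If 15% is an all-treated rate.** Suppose a share u of treated patients has no scan, none of them responded, and they are dropped while enrolment continues to 37 evaluable. The null rate among evaluable patients is then 0.15/(1 − u), and the formula in step 1 gives:

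| u | Null rate among evaluable | Early stop under the null | Type I error |
|---|---|---|---|
| 0 | 15.0% | 48.0% | 8.75% |
| 2% | 15.3% | 46.5% | 9.7% |
| 3% | 15.5% | 45.8% | 10.2% |
| 5% | 15.8% | 44.2% | 11.2% |
| 10% | 16.7% | 40.3% | 14.4% |

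Type I error crosses 10% at u of about 2.7%, where 0.15/0.973 = 0.154.

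**3. If the evaluable number is not 37.** Here 15% and 30% are rates among evaluable patients, and the 9-responder threshold is assumed to be applied to all n of them (stage 2 size n − 18):

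| n evaluable | Type I error | Power |
|---|---|---|
| 35 | 6.6% | 75% |
| 36 | 7.7% | 78% |
| 37 | 8.75% | 80.6% |
| 38 | 9.9% | 83% |
| 39 | 11.1% | 85% |
| 41 | 13.7% | 87% |

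With the evaluable number ~ Bin(41, 0.9), the probability of 39 or more is 0.135 + 0.061 + 0.013 = 0.21. The probability of fewer than 37 is 0.39.

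**4. All treated patients in the denominator, no scan counted as non-response.**

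- If 15% and 30% are all-treated rates, step 1 applies unchanged: type I error 8.75%, power 80.6%.
- If they are rates among evaluable patients and 10% are unscanned, the all-treated rates are 0.9 × 0.15 = 0.135 and 0.9 × 0.30 = 0.27. Type I error is then 5.1% and power 68.2%.

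**5. Replacement.** Sections 5.2.4 and 4.5.1/6.1.4 give opposite answers for the same patient. The plan gives no expected frequency of toxicity delays beyond 4 weeks, so no error-rate contribution can be calculated.

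**The case against.** A reader might infer that the plan simply fails its 10% limit. The documents do not support that. Taken as rates among evaluable patients, 15% and 30% reproduce the stated error rates, and an evaluable-patient denominator is a recognised choice in phase II. A breach needs two conditions: the 15% must be an all-treated rate, and more than about 2.7% of patients must be dropped as non-responders. The plan settles neither.

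The size is also limited.

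- The only share in the plan is 10%, and it pools ineligible patients, who may respond. If half of it were unscanned non-responders (an assumption) and the ineligible patients responded like the rest, type I error would be 11.2%, not 14.4%. Larger drop-out shares have no source in the documents.
- The end-of-study scan, and the final visit required of all who discontinue, will keep some early stoppers in. The life-expectancy criterion of 4 months or more also reaches beyond week 9.
- No section says that patients beyond 37 would be counted against the 9-responder threshold. Even if they were, 38 evaluable patients still give 9.9%.
- The replacement clause covers one narrow situation and is capped at the maximum enrolment.

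All of this stands, and it bears on the size. It does not settle the base of the 15%, say how a treated patient with no scan is counted, fix which 37 patients decide the trial, or reconcile the replacement rules.

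**Conclusion.** The concern holds as a lack of protection, not as a demonstrated breach. The decision set excludes treated patients without a RECIST-measurable scan, no rule counts them as non-responders, and the intent-to-treat set plays no part in the decision.

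Type I error is 8.75% if the 15% is a rate among evaluable patients. If it is an all-treated rate, type I error is 11.2% with 5% unscanned non-responders and at most 14.4% within the plan's 10% allowance. At that upper bound the chance of an early futility stop under the null falls from 48% to 40%.

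The conflict between evaluable and entered, and the conflict between replacing and not replacing, are in the text whatever the base of the 15%. The figures for 39 and 41 evaluable patients hold only if the 9-responder threshold is applied to everyone evaluable, which the plan does not say.

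**What to change.** Before the stage 1 decision, change sections 8.4.2 and 8.8 and the synopsis as follows, and align the wording of section 3.1.

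- **Denominator.** Base both decisions on patients who received at least one OBP-301 injection, in order of first dose: the first 18 for stage 1, then the first 37 with 9 or more responders for a positive result.
- **Missing response.** Count a treated patient with no response scan as a non-responder.
- **Sensitivity analysis.** Report the response rate in the evaluable set alongside.
- **Replacement.** Reconcile section 5.2.4 with sections 4.5.1 and 6.1.4 so that no treated patient leaves the efficacy denominator.
- **Base of the rates.** State whether 15% and 30% refer to all treated or to evaluable patients.

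**Cost.** The change is to wording. It needs no extra patients if 15% and 30% are all-treated rates (type I error 8.75%, power 80.6%). If they were meant among evaluable patients and 10% are unscanned, the same rule has type I error of about 5.1% and power of about 68%. The plan should then say so, and the sample size would have to be re-planned to restore 80% power.
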